9 STATISTICAL METHODS

This is a prospective, open-label, multicenter study of the patterns of variation in planar imaging using IV injected Tc 99m tilmanocept for the quantitative detection of disease activity in the skeletal joints of HC subjects and subjects with active RA. In addition to quantitative assessments, this study will also include qualitative (i.e., visual) evaluations of SPECT/CT in detecting localization within synovial spaces of the bilateral hands and wrists.

The study is stratified into 3 groups. Arm 1 consists of HC subjects. Arm 2 consists of RA patients on stable therapy. Arm 3 consists of RA patients who are candidates for initiation of, or change to, a new anti-TNF α bDMARD treatment.

9.1 Randomization Methods

This study is not randomized.

9.2 Safety Variables

The safety analysis variables are defined as follows:

- Adverse events (AEs)
- Clinical laboratory tests (hematology, serum chemistry, urinalysis, and RA panel)
- ECG parameters
- Vital signs

9.3 Efficacy Variables

The efficacy variables for this study are defined below:

- Quantitative determination of TUV_{joint} and TUV_{global}
- Qualitative (i.e., visual) evaluation of SPECT/CT in detecting localization within synovial spaces of the bilateral hands and wrists
- Subject RA status as summarized in the CDAI and ACR Response Criteria overall score and their constituent sub-scores

It is presumed that the presence of radiotracer uptake for a joint indicates the presence of activated macrophages. The use of the term “localization” is synonymous with radiotracer uptake.

The efficacy endpoints for this study, by arm, are as follows:

Primary Endpoint(s)

ARMS 1-2

- The camera-specific precision of TUV_{joint} and TUV_{global} in subjects with active RA and HCs, which is defined as the Root Mean Square Difference (RMSD) between the consecutive 15-minute planar images.

- The stability of the mean/variance relationship, which is assessed by comparing the Coefficient of Variation (CV) of TUV_{joint} and TUV_{global} in subjects with active RA and HCs.

ARM 2

- The longitudinal (8-day) precision of TUV_{joint} and TUV_{global} in subjects with active RA, which is defined as the RMSD of images at the same time point.

ARM 3

- The correlation of $\Delta TUV_{global[5w]}$ and response to new anti-TNF α bDMARD therapy defined by the change from baseline (CFB) of CDAI to 12 ± 1 weeks and 24 ± 1 weeks ($\Delta CDAI_{12w}$ and $\Delta CDAI_{24w}$, respectively). The correlation of $\Delta TUV_{global[5w]}$ and response to new anti-TNF α bDMARD therapy from baseline to 12 ± 1 weeks and 24 ± 1 weeks defined by ACR Response Criteria (ACR $_{12w}$ and ACR $_{24w}$, respectively).

Secondary Endpoint(s)

ARMS 1-2

- The temporal stability of the 150 mcg tilmanocept mass dose/10 mCi radiolabeling dose.

ARM 1

- The normal ranges of TUV_{joint} in HC subjects, which is defined as the 5 and 95 percentiles of:
 - TUV_{joint} of bilateral joints (i.e., bilateral wrists, MCPs, PIPs, knees, elbows, shoulders)

ARM 2

- The qualitative evaluations of SPECT/CT in detecting localization within synovial spaces of the bilateral hands and wrists.

ARM 3

- The correlation of the $TUV_{global[0week]}$ and response to new anti-TNF α bDMARD therapy defined by the change from baseline (CFB) of CDAI to 12 ± 1 weeks and 24 ± 1 weeks ($\Delta CDAI_{12w}$ and $\Delta CDAI_{24w}$, respectively) and by ACR Response Criteria (ACR $_{12w}$ and ACR $_{24w}$, respectively).
- The correlation of $\Delta TUV_{global[12w]}$ and $\Delta TUV_{global[24w]}$ and response to new anti-TNF α bDMARD therapy defined by the change from baseline (CFB) of CDAI to 12 ± 1 weeks and 24 ± 1 weeks ($\Delta CDAI_{12w}$ and $\Delta CDAI_{24w}$, respectively) and by ACR Response Criteria (ACR $_{12w}$ and ACR $_{24w}$, respectively).
- The correlation of $\Delta TUV_{global[5w]}$ and constituent parameters of $\Delta CDAI_{12/24w}$ and ACR $_{12/24w}$ including:
 1. Tender Joint Count (TJC)
 2. Swollen Joint Count (SJC)

3. Patient assessment of global disease activity
4. Rheumatologist assessment of global disease activity
5. Patient assessment of pain
6. Patient assessment of physical function
7. Acute-phase reactant value

9.4 Sample Size Justification

The study will enroll up to 105 evaluable subjects in Arms 1, 2, 3 allocated below, imaged at up to 10 study centers. Arm 1 will have N = 38 evaluable subjects, Arm 2 will have N = 38 evaluable subjects, and Arm 3 will have N = evaluable 29 subjects. A subject is considered evaluable if he/she meets the criteria for the analysis population and has the data necessary for computing the primary endpoint.

The sample size for Arm 1 was determined to assess temporal stability of the 150 mcg tilmanocept mass dose/10 mCi radiolabeling dose. The sample size for Arm 2 was determined to power the hypothesis test at 0.80. The sample size for Arm 3 was determined to provide a lower 97.5% confidence limit for the rank correlation of at most 0.15 when rho = 0.70, using Fisher's Z-transformation methods.

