 1. Planar scan of whole body
 2. Planar scan of bilateral hands and wrists
- Clinical labs (after imaging)
- RA-specific labs (after imaging)
- Urinalysis (after imaging)

Visit 9 (Follow-up Telephone Safety Assessment; 5 ± 3 Days After Visit 8)

- Review of concomitant medications
- AE assessment

*If a subject in Arm 3 requires early exit from the study between Week 16 and Week 24, an attempt should be made to complete a final imaging visit and all clinical assessments.

Test Product, Dose, and Mode of Administration:

Tc 99m tilmanocept will be administered through an IV route of injection. A 150-mcg dose containing 10 mCi of Tc 99m will be injected as a slow push into the IV catheter. At the completion of the injection, a 10-mL sterile normal saline flush will be administered. The preferred site of IV placement will be between the elbow and the wrist.

Planned Number of Study Centers:

Up to 10 centers in the United States

Sample Size:

105 evaluable subjects in Arms 1, 2, and 3 as allocated below. Arms 1 and 2 will have N = 38 evaluable subjects per Arm, and Arm 3 will have N = 29 evaluable subjects. A subject is considered evaluable if he/she meets the criteria for the analysis population and has the data necessary for computing the primary endpoint.

Rationale for Sample Size:

The sample size for Arm 1 was determined to provide sufficient data to quantify the precision of TUV in HCs. The sample size of Arm 2 was determined to power a hypothesis test of

$$H_0: \pi \leq 0.80$$

$$H_A: \pi > 0.80$$

at 80%. Here, π represents the fraction of the absolute differences less than 7.5%. The sample size for Arm 3 was determined to set the length of the lower 97.5% confidence limit for Spearman's rank correlation to be no more than 0.15.

After the injection, imaging, and quantitation of a total of 4 subjects in Arms 1 and 2, an interim analysis (interim analysis 1) will be held for the review of quantitative TUV results and assessment of imaging parameters and logistics. A second interim analysis (interim analysis 2) will be held after a total of 30 subjects (≥ 15 RA) in Arms 1 and 2 are injected, imaged, and quantified for the review of intra-and inter-subject TUV variation to contribute to the power analysis of a future Phase 3 study and/or to terminate the study on grounds of data sufficiency.

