The utility of $\Delta\text{TUV}_{\text{global}[5w]}$ to predict the subject's response to changed therapy will be assessed by computing the Kendall rank correlation between $\Delta\text{TUV}_{\text{global}[5w]}$ and $\Delta\text{ACAI}_{12w}, \Delta\text{ACAI}_{24w}, \Delta\text{ACR}_{12w}$, and ΔACR_{24w} . All times are relative to Study Day 0, and it is assumed that the new bDMARD therapy will begin after imaging on Day 0. A 95% confidence interval on the value of the rank correlation will be computed.

Date of Original Approved Protocol: 16 November 2018

TABLE OF CONTENTS

SYNOPSIS.....	2
LIST OF IN-TEXT TABLES	20
LIST OF IN-TEXT FIGURES.....	20
LIST OF APPENDICES.....	21
LIST OF ABBREVIATIONS AND DEFINITIONS OF TERMS.....	22
1 INTRODUCTION	25
1.1 Background	25
1.2 Previous Nonclinical Research and Clinical Trial Experience in Tc 99m Tilmanocept	30
1.2.1 Nonclinical Evaluations –Subcutaneous Administration.....	30
1.2.2 Nonclinical Evaluations – IV Administration.....	30
1.2.3 Clinical Pharmacokinetics (IV).....	32
1.2.4 Clinical Efficacy	33
1.2.4.1 NAV3-23 (SC)	33
1.2.4.2 NAV3-21 (IV).....	34
1.2.5 Clinical Safety.....	34
1.2.5.1 NAV3-23 (SC)	34
1.2.5.2 NAV3-21 (IV).....	34
2 STUDY OBJECTIVES.....	35
2.1 Primary Objective(s).....	35
2.2 Secondary Objective(s).....	35
2.3 Safety Objective(s).....	35
3 INVESTIGATIONAL PLAN	36
3.1 Overall Study Design and Plan	36
3.1.1 Arm 1: No Inflammatory and/or Joint Disease (HC Subjects)	36
3.1.1.1 Description of Patient Population	36
3.1.1.2 Overview of Study Procedures	36
3.1.1.3 Justification for Population.....	36
3.1.2 Arm 2: Stable Anti-Rheumatic Therapy (RA Subjects)	37
3.1.2.1 Description of Patient Population	37
3.1.2.2 Overview of Study Procedures	37
3.1.3 Arm 3: Change in anti-TNF α bDMARD Therapy (RA Subjects).....	38
3.1.3.1 Description of Patient Population	38
3.1.3.2 Overview of Study Procedures	38
3.1.3.3 Justification for Population	38
3.2 Protocol Adherence.....	38
3.3 Study Duration(s).....	39
4 STUDY POPULATION	40

4.1	Study Arms	40
4.2	Eligibility	40
4.2.1	Inclusion Criteria	40
4.2.2	Exclusion Criteria	41
4.3	Recruitment.....	41
4.4	Withdrawal.....	42
4.5	Replacement.....	42
4.6	Screen Failures.....	42
4.7	Subject Identification.....	42
5	INVESTIGATIONAL PRODUCT.....	44
5.1	Description of Investigational Product	44
5.2	Investigational Product Dosage and Administration	44
5.3	Timing and Frequency of Drug Administration	45
5.4	Packaging and Labeling.....	46

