9.5.3 Analysis of Efficacy Variables

All efficacy analyses will be conducted on both the ITD and PP populations. The ITD population will be the primary analysis set.

9.5.3.1 Primary Endpoints Arms 1- 2

Precision endpoints will be assessed estimating the mean, standard deviation, n, minimum, median, and maximum of the signed differences, calculated as change from the initial measurement. The RMSD will be calculated and a 95% confidence interval on its value will be provided.

Stability of the mean/variance relationship will be assessed by the coefficient of variation of the differences for active RA subjects and HC subjects at 60 minutes and 180 minutes. 95% confidence intervals for the difference in CVs following the methods of ([Forkman 2009](#)) and from the bootstrap sampling distribution of the difference of the CVs will be provided based on N = 5000 bootstrap samples.

9.5.3.2 Secondary Endpoints Arms 1- 2

The normal ranges of ΔTUV_{joint} will be estimated from data collected from HC subjects (Arm 1 only) at 60 minutes and 180 minutes post-injection. The mean, standard deviation, n (number of joints), and quantile regression estimates of the 5 and 95 percentiles will be provided for shoulder, elbow, wrist, MCP, PIP, and knee.

9.5.3.3 Primary endpoint Arm 3

The Kendall rank correlation between $\Delta TUV_{global[5w]}$ with $\Delta CDAI_{12w}$ and $\Delta CDAI_{24w}$ will be computed and a 95% confidence interval for its value will be computed using Fisher's Z-transformation. Similarly, the Kendall rank correlation between $\Delta TUV_{global[5w]}$ with ΔACR_{12w} and ΔACR_{24w} (overall scores only) will be computed and a 95% confidence interval for its value will be computed using Fisher's Z-transformation.

9.5.3.4 Secondary endpoint Arm 3

The Kendall rank correlations between $\Delta TUV_{global[5w]}$ with the subscores of ΔACR_{12w} and ΔACR_{24w} (including tender joint count, swollen joint count, Patient assessment of global disease activity, Rheumatologist assessment of global disease activity, Patient assessment of pain, Patient assessment of physical function, Acute-phase reactant value) will be computed and a 95% confidence interval for its value will be computed using Fisher's Z-transformation.

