The Kendall rank correlations between $TUV_{global[0w]}$, $\Delta TUV_{global[12w]}$, $\Delta TUV_{global[24w]}$ with the $\Delta CDAI_{12w}$, $\Delta CDAI_{24w}$, ΔACR_{12w} , ΔACR_{24w} will be computed and a 95% confidence interval for their values will be computed using Fisher's Z-transformation.

Additional efficacy analyses may be described in the Statistical Analysis Plan (SAP) for the study.

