1.3 Sample Size

Up to 105 subjects from up to 10 study centers will be enrolled into Arms 1, 2, and 3 as allocated below, and imaged. Arm 1 will have N = 38 evaluable subjects, Arm 2 will have N = 38 evaluable subjects, and Arm 3 will have N = 29 evaluable subjects. A subject is considered evaluable if he/she meets the criteria for the analysis population and has the data necessary for computing the primary endpoint.

The sample size for Arm 1 was determined to assess temporal stability of the 150 μ g mass dose/10mCi radiolabeling dose. The sample size for Arm 2 was determined to power a hypothesis test at 0.80:

$$\begin{aligned} H_0: \pi &\leq 0.80 \\ &\text{vs} \\ H_a: \pi &> 0.80, \end{aligned}$$

where π represent the fraction of unsigned differences less than 7.5% The sample size for Arm 3 was determined to provide a lower 97.5% confidence limit for the rank correlation of at most 0.15 when $\rho = 0.70$, using Fisher's Z-transformation methods.

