The Kendall rank correlation between $\Delta TUV_{global[5w]}$ with $\Delta CDAI_{12w}$ will be computed and a 95% confidence interval for its value will be computed using Fisher's Z-transformation. Similarly, the Kendall rank correlation between $\Delta TUV_{global[5w]}$ with changes from baseline in each of the ACR Response Criteria components at 12 weeks (tender joint count (TJC), swollen joint count (SJC), patient assessment of global disease activity, rheumatologist assessment of global disease activity, patient assessment of pain, patient assessment of physical function, and acute-phase reactant value) will be computed and a 95% confidence interval for its value will be computed using Fisher's Z-transformation.

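### The stated basis for Arm 3's N = 29 is false as written and differs between the synopsis and Protocol 9.4/SAP 1.3; 29 itself may be sound, but its derivation is not documented

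*Protocol*

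**What the plan says.** Three places give a basis for Arm 3's 29 evaluable subjects.

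- **Protocol 9.4** says the number was chosen to provide "a lower 97.5% confidence limit for the rank correlation of at most 0.15 when rho = 0.70", using Fisher's Z.
- **SAP 1.3** agrees, with a "confidence limit for the rank correlation of at most 0.15" at the same rho and by the same method. Neither section says which rank correlation is meant, or whether 0.70 is a Pearson, Spearman or Kendall value.
- **Protocol synopsis, Rationale for Sample Size**, says the Arm 3 number "was determined to set the length of the lower 97.5% confidence limit for" Spearman's "rank correlation to be no more than 0.15". It gives no assumed correlation.

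The planned analysis is Kendall's throughout. In the synopsis (Statistical Methods, Arm 3) the utility of the week-5 TUV change "will be assessed by computing the Kendall rank correlation between" it and the clinical changes. Protocol 9.5.3.3 and SAP 4.1.1 and 4.2.1 also specify Kendall.

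The interval is described only by its transformation. In Protocol 9.5.3.4 the Kendall correlations "will be computed and a 95% confidence interval for their values will be computed using" Fisher's Z, and SAP 2.5 (Arm 3 Only) has the same form: "will be computed and a 95% confidence interval for its value will be computed using" that transformation. No standard error is given in either document.

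**The concern.** A precision target for a correlation should put a floor under the lower confidence limit, or a ceiling on its distance from the estimate. A ceiling on the limit itself is met by small samples and broken by large ones, so it cannot lead to a sample size. The synopsis differs again in both target and coefficient.

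No power is stated for Arm 3, so this is the only recorded reason for 29. A reader of the study report could not tell what precision was intended, or for which statistic. The unstated standard error is a smaller matter of the same kind: two programmers following the SAP could report different Arm 3 primary intervals from the same data.

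**Working it through.** **Inputs from the documents.** n = 29; assumed correlation 0.70; threshold 0.15; lower 97.5% limit (the lower end of a two-sided 95% interval, multiplier 1.96); Fisher's Z.

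**Assumptions, not in the documents.** The standard errors 1/√(n−3) (ordinary Fisher) and √(0.437/(n−4)) (a common choice for Kendall), and the bivariate-normal conversion tau = (2/π)·arcsin(rho).

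**Formula.** Lower limit L = tanh(atanh(r) − 1.96·SE).

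**1. The sentence as written, 0.70 used directly.** atanh(0.70) = 0.8673. At n = 29, 1.96/√26 = 0.3844, so L = tanh(0.4829) = 0.449. L is 0.126 at n = 10 and 0.173 at n = 11, so *at most 0.15* holds only for n of 10 or fewer.

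**2. The sentence as written, 0.70 converted to Kendall.** tau = (2/π)·arcsin(0.70) = 0.494, and atanh(tau) = 0.5408. At n = 29, L = tanh(0.5408 − 0.3844) = 0.155. This too exceeds 0.15. At n = 28 it is 0.148, so the ceiling is met by 28 subjects and broken by 29.

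**3. Can 29 be reproduced?** Reverse the direction to *at least 0.15* and keep tau = 0.494 with 1/√(n−3). With atanh(0.15) = 0.1511:

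n = 3 + [1.96/(0.5408 − 0.1511)]² = 28.3, which rounds up to 29.

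This uses every figure in Protocol 9.4 and the planned statistic. It is not the only route to 29:

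- 95% power for 0.70 against 0.15, two-sided 5%: n = 3 + [(1.960 + 1.645)/(0.8673 − 0.1511)]² = 28.3, so 29. The documents state no power for Arm 3.
- Distance from 0.70 up to the *upper* limit of at most 0.15: 0.1509 at n = 28 and 0.1488 at n = 29, so 29. The documents speak of the lower limit.

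Reversing the direction alone is not enough. With 0.70 used directly, *at least 0.15* needs only n = 11.

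**4. The synopsis target.** Without a stated correlation it cannot be checked. If 0.70 is carried over (an assumption), the distance from estimate to lower limit at n = 29 is 0.700 − 0.449 = 0.251, against 0.15.

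**5. The standard error for the Kendall interval, n = 29, tau = 0.494.**

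| SE on z scale | Value | 95% interval |
|---|---|---|
| 1/√(n−3) | 0.196 | 0.155 to 0.728 |
| √(0.437/(n−4)) | 0.132 | 0.274 to 0.664 |

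The ratio is 0.196/0.132 = 1.48. In simulation (n = 29, continuous bivariate-normal data, rho from 0 to 0.70), coverage was above 99% with 1/√(n−3), 94.7–94.9% with √(0.437/(n−4)), and 94.1–94.3% with the tau-b asymptotic SE. With an assumed tied outcome (about 8 to 13 distinct values among 29 subjects), 1/√(n−3) was 38–43% too wide. Coverage was then 93.3–94.0% with √(0.437/(n−4)) and 94.0–94.5% with the tau-b asymptotic SE.

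**The case against.** The best defence is that this is a one-word slip. Write *at least* for *at most*, read rho = 0.70 as a bivariate-normal correlation, convert it to Kendall's tau, and Fisher's Z returns exactly 29. On that reading the number was properly derived for the statistic that is analysed. The general term used in Protocol 9.4 and SAP 1.3 is compatible with Kendall; only the synopsis says Spearman.

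Much of this stands. A reader might infer that 29 has no valid basis, or that the target was set for the wrong coefficient throughout. The documents do not support either inference. A reader might also apply 0.70 to the synopsis target and conclude that Arm 3 is too small: depending on the coefficient and standard error assumed, that calculation asks for anything from 32 to 81 subjects. But the synopsis states no correlation, so the range measures a combined target that the sponsor did not write.

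What does not stand is that the slip can be corrected without asking the sponsor. The conversion to tau is not written anywhere, and at least two other unstated readings also give 29. Editing one word would record a guess.

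On the interval, it is fair to say that 1/√(n−3) errs on the conservative side and threatens no conclusion, since Arm 3's primary correlations are estimated with an interval and not tested against a threshold.

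**Conclusion.** The point holds as an error of statement and consistency. In Protocol 9.4 and SAP 1.3 the claimed limit of at most 0.15 is actually 0.449 or 0.155 at n = 29, depending on whether 0.70 is taken as the analysed coefficient or converted to tau = 0.494. The inequality runs the wrong way under either reading. The synopsis states a different target for a different coefficient from the one analysed. These results assume SE = 1/√(n−3), which the documents do not specify.

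It does not follow that 29 is wrong or unsupported. A coherent Kendall derivation gives exactly 29; what is missing is the sponsor's confirmation that it was the one used.

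The unstated standard error is a secondary point. If 1/√(n−3) were used for tau, intervals would be about 48% too wide on the z scale for continuous data. That loses information but does not threaten validity. The point should be fixed, and it is no reason to change the sample size.

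**What to change.** Keep N = 29.

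1. **Sample-size sentence.** The sponsor should confirm how 29 was obtained. Then use one identical sentence about Kendall's tau in the synopsis, Protocol 9.4 and SAP 1.3. If the Kendall derivation is confirmed, for example: *N = 29 gives a lower 97.5% confidence limit of at least 0.15 for Kendall's tau when tau = 0.494 (bivariate-normal rho = 0.70), using Fisher's Z with SE 1/√(n−3).* Otherwise state the actual basis, or the expected interval at n = 29.
2. **Interval method (secondary).** In Protocol 9.5.3.3–9.5.3.4 and SAP 2.5, 4.2.1 and 4.2.2, name the standard error and use one suited to Kendall: the tau-b asymptotic SE divided by (1 − tau-b²) on the z scale, or √(0.437/(n−4)) where ties are few. The expected interval at tau = 0.494 is then about 0.27 to 0.66. The planning sentence should say that 1/√(n−3) was a conservative planning choice, because with √(0.437/(n−4)) the 0.15 floor would need only 16 subjects. The small downside is coverage slightly under 95% with the asymptotic SE. A bootstrap interval alongside is optional.

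The cost is one sentence in three places, one sentence on the standard error in each document's methods, and a few lines of code.

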9.5 Statistical Analyses

9.5.1 Analysis Populations

The following populations are defined for this study:

Intent-to-Diagnose (ITD) Population – the ITD population includes all subjects who have been enrolled in the study, injected with Tc 99m tilmanocept, and received all imaging and evaluations necessary for the primary endpoint(s) appropriate to their respective arm.

Per-Protocol (PP) Population – the PP population consists of all ITD subjects without major protocol violations.

Safety Population – The safety population includes all subjects who have been enrolled in the study and injected with at least 1 dose of Tc 99m tilmanocept.

9.5.2 Analysis of Baseline and Demographic Characteristics

Baseline and demographic characteristics of the safety population will be summarized by subject status and overall. Continuous variables (age, height, and weight) will be summarized via mean, standard deviation, minimum, maximum, and number of non-missing responses. Categorical variables (gender, race and ethnicity) will be summarized via counts and percentages.

9.5.3 Analysis of Efficacy Variables

All efficacy analyses will be conducted on both the ITD and PP populations. The ITD population will be the primary analysis set.

9.5.3.1 Primary Endpoints Arms 1- 2

Precision endpoints will be assessed estimating the mean, standard deviation, n, minimum, median, and maximum of the signed differences, calculated as change from the initial measurement. The RMSD will be calculated and a 95% confidence interval on its value will be provided.

Stability of the mean/variance relationship will be assessed by the coefficient of variation of the differences for active RA subjects and HC subjects at 60 minutes and 180 minutes. 95% confidence intervals for the difference in CVs following the methods of ([Forkman 2009](#)) and from the bootstrap sampling distribution of the difference of the CVs will be provided based on N = 5000 bootstrap samples.

9.5.3.2 Secondary Endpoints Arms 1- 2

The normal ranges of ΔTUV_{joint} will be estimated from data collected from HC subjects (Arm 1 only) at 60 minutes and 180 minutes post-injection. The mean, standard deviation, n (number of joints), and quantile regression estimates of the 5 and 95 percentiles will be provided for shoulder, elbow, wrist, MCP, PIP, and knee.

9.5.3.3 Primary endpoint Arm 3

The Kendall rank correlation between $\Delta TUV_{global[5w]}$ with $\Delta CDAI_{12w}$ and $\Delta CDAI_{24w}$ will be computed and a 95% confidence interval for its value will be computed using Fisher's Z-transformation. Similarly, the Kendall rank correlation between $\Delta TUV_{global[5w]}$ with ΔACR_{12w} and ΔACR_{24w} (overall scores only) will be computed and a 95% confidence interval for its value will be computed using Fisher's Z-transformation.

9.5.3.4 Secondary endpoint Arm 3

The Kendall rank correlations between $\Delta TUV_{global[5w]}$ with the subscores of ΔACR_{12w} and ΔACR_{24w} (including tender joint count, swollen joint count, Patient assessment of global disease activity, Rheumatologist assessment of global disease activity, Patient assessment of pain, Patient assessment of physical function, Acute-phase reactant value) will be computed and a 95% confidence interval for its value will be computed using Fisher's Z-transformation.

The Kendall rank correlations between $TUV_{global[0w]}$, $\Delta TUV_{global[12w]}$, $\Delta TUV_{global[24w]}$ with the $\Delta CDAI_{12w}$, $\Delta CDAI_{24w}$, ΔACR_{12w} , ΔACR_{24w} will be computed and a 95% confidence interval for their values will be computed using Fisher's Z-transformation.

Additional efficacy analyses may be described in the Statistical Analysis Plan (SAP) for the study.

